12.1.4 Test of Superiority for Lesion Count Variables

This section provides the basic model and statistical approach which is used in combination with the multiple imputation procedures described in Section 12.1.7. Tests of superiority for the absolute change from Baseline in inflammatory and non-inflammatory lesions will be based on either parametric or non-parametric methods consistent with the statistical assumptions required to support the analyses. Specifically, the tests of superiority will be based on an ANCOVA with factors of treatment and analysis center and the respective Baseline lesion count as a covariate or on ranked data submitted to an ANCOVA with factors of treatment and analysis center and the respective Baseline lesion count as a covariate. If the treatment-by-analysis center interaction effect is significant at an alpha less than 0.10, then the effect will be included in the model; otherwise it will be removed.

A skewness test, based on the methods presented by J.H. Zar (1984) [10], will be applied to the residuals resulting from an ANCOVA. A two-sided p-value for the skewness test significant at

0.01 will imply the use of the non-parametric method. If a parametric analysis is indicated, the results of the parametric analysis will be considered the primary analysis. Should a non-parametric analysis be indicated, the absolute or percent changes in inflammatory and non-inflammatory lesions will be rank transformed prior to submitting them to the ANCOVA. Results of the rank-transformed analyses then will be considered the primary analysis; however, results of the non-ranked transformed analyses will also be presented.

12.1.5 Statistical Hypothesis Testing and Control of Multiplicity

Statistical hypothesis testing for lesion count analyses will use the statistical model introduced in Section 12.1.3 and employs the methods of Section regarding missing values. The analysis of the dichotomized Evaluator's Global Severity Score will be based on the logistic regression test stratified by analysis center and employs the methods of Section 12.1.7 regarding missing values.

The overall Type I error will be controlled by requiring the co-primary efficacy endpoints of each group to be statistically significant. Specifically, failure of any one of the primary efficacy endpoints will invalidate the statistical significance of the secondary efficacy endpoints.

The following stepwise process will be conducted for testing the secondary efficacy endpoints in order to control for multiplicity. These tests will be performed for only the ITT population. The testing process will terminate whenever a statistical test for a step is not significant. All subsequent tests for the remaining steps will be considered not significant. The order of testing is:

Step Number	Secondary Endpoint
1	Percent change in non-inflammatory lesion count from baseline to Week 12
2	Percent change in inflammatory lesion count from baseline to Week 12

The following stepwise process will be conducted for testing the supportive efficacy endpoints in order to control for multiplicity. These tests will be performed for only the ITT population. In order to control for multiplicity failure of any one of the secondary efficacy endpoints will invalidate the statistical significance of the supportive efficacy endpoints. The testing process will terminate whenever a statistical test for a step is not significant. All subsequent tests for the remaining steps will be considered not significant. The order of testing is:

Step Number	Supportive Endpoint
1	Percent change in non-inflammatory lesion count from baseline to Week 8
2	Percent change in inflammatory lesion count from baseline to Week 8
3	Percent change in non-inflammatory lesion count from baseline to Week 4
4	Percent change in inflammatory lesion count from baseline to Week 4
5	Proportion of subjects who have at least a 2 grade reduction at Week 12 from

	baseline in the Evaluator's Global Severity Score
6	Proportion of subjects who have at least a 2 grade reduction at Week 8 from baseline in the Evaluator's Global Severity Score
7	Proportion of subjects who have at least a 2 grade reduction at Week 4 from baseline in the Evaluator's Global Severity Score

12.1.6 Descriptive Statistics

Descriptive statistics will be presented for the following parameters by treatment group for both the ITT and PP populations:

- Frequency and percent distributions of the Evaluator's Global Severity Score at Baseline and Weeks 4, 8, and 12.
- Frequency and percent distributions of the dichotomized Evaluator's Global Severity Score at Baseline and Weeks 4, 8, and 12.
- Descriptive statistics including mean, median, standard deviation, minimum, and maximum will be used to summarize inflammatory and non-inflammatory lesion counts at baseline and weeks 4, 8, and 12.
- Descriptive statistics including mean, median, standard deviation, minimum, and maximum will be used to summarize the absolute and percent change in inflammatory and non-inflammatory lesion counts at Weeks 4, 8, and 12.
- Frequency and percent distributions for the Oily/Shiny assessments at Week 12

Means, standard deviations and frequency counts (rounded to the nearest whole number) will be computed from the multiply imputed MCMC data for the variable.

12.1.7 Pooling Analysis

The clinical study will be conducted under a common protocol for each investigational site with the intention of pooling the data for analysis. Every effort will be made to promote consistency in study execution at each investigational site. The study is intended to be conducted in a manner such that a minimum of 5 subjects will be enrolled in each treatment arm for any investigator. In the event that there are too few subjects in a treatment arm for an investigator, then this investigator's data will be combined to achieve the desired sample size minimum per arm. The combining of investigator's data will be accomplished by taking the investigator with the smallest enrollment and combining it with the investigator with the largest. If there is a further need to combine data, then the data of the investigator with the second smallest enrollment will be combined with the investigator's data which had the second largest enrollment, and so on. This process will continue for all investigators who did not have a minimum of 5 subjects per active treatment arm. The process of combining investigator data that have insufficient subjects per treatment arm will result in redefining the groups of investigators for the purposes of

statistical analyses. These combined groups will be referred to as "analysis centers" in the statistical analyses based on ANCOVA and stratified logistic testing.

Prior to investigating the treatment effect within the analysis centers, the magnitude of the site mail effect will be investigated to determine if the main site-to-site variability is such that it could mask the analysis center effects. Thus, if computationally possible, a one-way ANCOVA (for lesion count variables) or a logistic regression analysis (for EGSS) with a factor of site will be conducted prior to pooling. If the data structure interferes with the logistic regression, a descriptive analysis of the site effect will be undertaken. Conclusions appropriate to the findings of this step will be presented.

The consistency of treatment response will be investigated across the analysis centers subsequent to combining the data as described above. Statistical tests will be conducted to identify if there are extreme analysis centers that could affect the interpretation of common statistical and clinical conclusions. An analysis center by treatment interaction will be included in the primary and secondary variable analyses to test for parallel treatment effect at an alpha level of 0.10. Change from baseline in inflammatory lesions and non-inflammatory lesions will be analyzed with an ANCOVA (unranked or ranked) with factors of treatment, analysis center, and treatment by analysis center interaction and the respective baseline lesion count variable as a covariate. For the purpose of testing consistency of treatment response, the dichotomized EGSS will be analyzed with a logistic regression procedure. Further examination will follow for any variables that have a significant ANCOVA or logistic regression interaction term. In the event that the ANCOVA or logistic regression interaction (referred to henceforth as the "appropriate test") p-value is less than or equal to 0.10, a sensitivity analysis that excludes analysis centers with the extreme efficacy result will be performed to determine the robustness of the treatment effect. On the other hand, if the outcome of the appropriate test has a p-value greater than 0.10, then the conclusions from the pooled data will be considered to be free of the impact of extreme analysis centers.

The first step in conducting a sensitivity analysis is to identify the extreme analysis center or centers that contribute to the statistical significance of the appropriate test. The process involves submitting subsets of analysis centers to the appropriate test and observing the appropriate test p-value for the subset. Subsets with p-values greater than 0.10 for the appropriate test are considered homogeneous.

The search for an extreme analysis center begins by analyzing all subsets that can be created by excluding one analysis center. If one or more of the subsets result in an appropriate test p-value greater than or equal to 0.10, then the analysis center excluded from the subset with the largest p-value for the appropriate test is deemed to be the extreme analysis center.

If all appropriate test subset p-values are less than or equal to 0.10, then the process will analyze the appropriate test for all subsets that can be created by excluding two analysis centers. If one

or more of these subsets generate appropriate test p-values larger than 0.10, then the analysis centers excluded from the subset with the largest appropriate test p-value are deemed the extreme analysis centers.

Thus, the process of identifying the extreme analysis centers will continue in a stepwise manner by first excluding one, then two, then three, etc., analysis centers until the appropriate test p-value exceeds 0.10.

Once the extreme analysis center or centers have been identified, then the treatment p-values of the remaining analysis centers will be computed. Inferences will be drawn from the treatment p-value, as well as any pertinent observations regarding the extreme analysis center or centers.

Additionally, it is noted that this process excludes subjects from the analysis in a non-random manner and has an unpredictable impact on the power of the treatment effect test. In the event that the treatment effect of the remaining subset is not statistically significant, due consideration of the post-hoc aspects of the process will be given when the results are interpreted. Conclusions will be presented by the sponsor as appropriate to the findings of the sensitivity analysis.

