7.1 Overall Study Design and Plan: Description

This is a multicenter, randomized, double-blind, parallel-group study designed to assess the safety, efficacy and tolerability of IDP-121 Lotion in comparison with its vehicle. To be eligible for the study, subjects must be at least 9 years of age and older and have a clinical diagnosis of moderate to severe acne vulgaris (a score of 3 or 4 [moderate to severe] on the EGSS scale).

Approximately 800 subjects will be enrolled into this study and randomized into one (1) of two (2) treatment groups: 400 subjects in the IDP-121 Lotion, once daily application group, Version 4, 7 October 2016

CONFIDENTIAL

and 400 subjects in the IDP-121 Lotion Vehicle, once daily application group. Subjects will be enrolled at a minimum of 32 and maximum of 50 independent study centers. The duration of treatment will be 12 weeks. Subjects will be evaluated at Screening, Baseline and at subsequent follow-up visits (Weeks 4, 8, and 12).

An interactive web based response system (IWRS) will be employed to facilitate randomization of study patients. Treatment assignments and study drug kit numbers will be generated centrally by the IWR system. At each clinical site, subject numbers will be assigned consecutively at the screening visit starting with 001.

The assigned study drug will be applied topically to the face once daily for 12 weeks (up to week 12 visit). The initial application will be made at the investigational center as per instruction from the study coordinator or designee. The subjects will be instructed to avoid exposure to direct sunlight to prevent sunburn. Subjects will apply their daily treatments at home as explained by the study coordinator or designee at each investigational center. During post-baseline study visits (Weeks 4, 8 and 12) the subjects will be asked to return their used tubes of study drug and will be dispensed new tubes of study drug (only Weeks 4 and 8; Week 12 will be final visit). During the study, each subject will only be permitted to use approved non-medicated cleansers, moisturizers and sunscreens.

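### For the lesion counts, a treatment-by-center interaction p above 0.10 cannot support the plan's statement that the pooled conclusions are free of extreme-center impact

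*Combined protocol and SAP*

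**What the plan says.** Section 12.1.7 (Pooling Analysis) first builds analysis centers. The aim is that "a minimum of 5 subjects will be enrolled in each treatment arm for any investigator". Investigators below that minimum are pooled by "taking the investigator with the smallest enrollment and combining it with the investigator with the largest", then second smallest with second largest, and so on.

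For the lesion counts it then fits an "ANCOVA (unranked or ranked) with factors of treatment, analysis center, and treatment by analysis center interaction", with the baseline count as covariate, "to test for parallel treatment effect at an alpha level of 0.10". Two branches follow:

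- If p is 0.10 or less, "a sensitivity analysis that excludes analysis centers with the extreme efficacy result will be performed to determine the robustness of the treatment effect".
- If p is above 0.10, "then the conclusions from the pooled data will be considered to be free of the impact of extreme analysis centers".

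The second branch sets no margin and asks for no interval, by-center estimate or measure of influence. Section 12.8.2 gives power for the main treatment comparisons. The documents give none for the interaction test.

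**The concern.** The second branch turns a non-significant test into a positive statement that centers had no impact. That would be reasonable only if the test would probably have been significant had a center deviated enough to matter. Here the test spreads its degrees of freedom over many small centers, so p above 0.10 is the expected outcome whether or not one center deviates.

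Nothing else in the plan fills the gap when p is above 0.10. The pre-pooling check in 12.1.7 models site alone and does not look at treatment effects by site. The analyses in 12.1.9 deal with missing data. The US versus outside-US split in 12.1.10 is descriptive and far coarser than a center. The report could therefore claim freedom from center influence without having examined it.

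**Working it through.** **Inputs from the protocol.** Section 7.1: "Approximately 800 subjects will be enrolled into this study", "enrolled at a minimum of 32 and maximum of 50 independent study centers". Section 9.1: 1:1 allocation. Section 12.1.7: interaction alpha 0.10 and at least 5 per arm. Section 12.8.2: inflammatory change 6.5 versus 3.5, SD 11.3; non-inflammatory change 17.8 versus 9.9, SD 24.7. Pairing all of 32 sites would leave 16 analysis centers; no pooling at 50 sites leaves 50. So K runs from 16 to 50.

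**Assumed, not in the documents.** One deviating center, its effect off by δ = 0.5 SD, and equal center sizes unless stated. In lesions, 0.5 × 11.3 = 5.65 and 0.5 × 24.7 = 12.35. The planned effects are 3.0/11.3 = 0.27 SD and 7.9/24.7 = 0.32 SD, so δ exceeds both.

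**The plan's own power figures reproduce.** Power ≈ Φ(Δ/(SD·√(2/400)) − 1.96).

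- Inflammatory: 3.0/0.799 = 3.75, giving 96.4% (plan: at least 96%).
- Non-inflammatory: 7.9/1.747 = 4.52, giving 99.5% (plan: greater than 99%).

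**Power of the interaction test.** It is an F test on K − 1 and 800 − 2K − 1 df. If one center of n₁ subjects is off by δ, the non-centrality is λ = δ²·(n₁/4)·(1 − n₁/800). For K = 32, n₁ = 25: λ = 0.25 × 6.25 × 0.969 = 1.51.

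| K (equal centers) | n₁ | λ | P(p > 0.10) |
|---|---|---|---|
| 16 | 50 | 2.93 | 77.4% |
| 20 | 40 | 2.38 | 81.3% |
| 25 | 32 | 1.92 | 84.0% |
| 32 | 25 | 1.51 | 86.1% |
| 40 | 20 | 1.22 | 87.3% |
| 50 | 16 | 0.98 | 88.1% |
| no deviating center | – | 0 | 90% |

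Simulating the ANCOVA (1,000 runs each) gives 85.1% at K = 32 and 87.5% at K = 50. With effective N of 680–720 to allow for missing data, the rate at K = 32–50 is still 86.5–88.4%.

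**How the rate moves.**

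- Center of 100 subjects off by 0.5 SD: missed 73% (K = 32) to 77% (K = 50) of the time.
- Center of 160 subjects off by 0.5 SD: 64% to 70%.
- Average-sized center off by 1.0 SD: 71% to 81%.
- Every center off the mean by 0.25 SD: 46% to 56%, so broad heterogeneity is seen better.

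**Effect on the pooled difference.** The shift is δ·n₁/800.

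- K = 50: 0.5 × 16/800 = 0.010 SD, or 0.11 inflammatory lesions (0.113/3.0 = 3.8%) and 0.25 non-inflammatory (0.247/7.9 = 3.1%).
- K = 16: 0.5 × 50/800 = 0.031 SD, or 0.35 inflammatory (0.353/3.0 = 11.8%) and 0.77 non-inflammatory (0.772/7.9 = 9.8%).

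Hence about 3–12% of plan. A 100-subject center would shift the inflammatory difference by 0.71 lesions (0.706/3.0 = 24%).

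**Dependence on one center.** This was simulated with 400 per arm, uneven gamma-multinomial site sizes (assumed) and pooling of sites below 5 per arm, which leaves about 28–36 analysis centers. The largest center was set 0.5 SD higher. At the planned inflammatory effect, significance is lost on removing that center in about 4–5% of trials; with no deviating center the figure is 1–2%.

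**The case against.** The strongest reply is that the sentence concerns the conclusions from the pooled data, not equality of every center. Missing a deviating center is an error in that sense only if the center alters the pooled conclusion, and an average-sized one hardly does. The 0.5 SD benchmark is assumed and larger than the whole planned effect. The screen changes neither the primary test's alpha nor the sample size, and the section itself warns that the exclusion step is non-random and post hoc. All of this stands, and it limits the consequence. It does not rescue the inference: if influence is small, by-center and leave-one-out estimates would show that, and the interaction p-value does not.

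A reader might infer three stronger things that the documents do not support.

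- **That a significant primary result probably rests on one center.** This needs an off-plan scenario. With a true effect of only 0.1 SD elsewhere (about 1.1 inflammatory lesions against a planned 3.0) and the largest center 0.5 SD higher, 19–26% of trials are significant only because of that center, and the rule passes 72–80% of those. Neither assumption is in the documents.
- **That no robustness analysis would be run.** Repeated-measures and model-based imputation analyses (12.1.9) and a supportive per-protocol analysis (12.1) run whatever the interaction result. Only center exclusion is conditional.
- **That the test's level is wrong.** For the unranked ANCOVA it is about 10%, as intended. The weakness is power.

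**Conclusion.** The concern holds as a fault of inference. For the lesion counts, p above 0.10 is nearly as likely with one center off by 0.5 SD (about 77–88%) as with none (90%), so it cannot support a statement of no impact. This rests on a single deviating center, roughly equal center sizes, 16–50 analysis centers, 800 subjects and the unranked ANCOVA. The rate falls for a much larger center, for fewer centers, or for heterogeneity spread over many centers.

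The plan's figures do not point to a likely reversal of the primary result. What is at stake is an assurance in the report that the planned analysis cannot give. It would matter most if the true effect fell well short of plan or one center enrolled a large share of subjects.

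**What to change.** In section 12.1.7, and in any matching SAP text, delete the sentence that equates p above 0.10 with freedom from extreme-center impact. For each lesion-count co-primary, whatever the interaction p-value:

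1. Report the treatment difference with 95% CI by analysis center.
2. Report the leave-one-analysis-center-out range of the pooled difference, as estimate and 95% CI.
3. Describe center influence by the size of the shift in the estimate, and keep the interaction p-value as descriptive.

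Influence should not be judged by whether p stays below 0.05 with each center removed. Under the same simulation assumptions, significant trials fail that check about as often without a deviating center as with one: 42–47% versus 46–52% at a true effect of 0.1 SD, and 6–7% versus 4–5% at 0.265 SD. It mainly reflects how close the pooled p-value is to 0.05.

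The cost is a wording change and one extra table or figure per endpoint, with no new data, subjects or alpha. A dominant center, if there is one, would be visible in the report.

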A similar procedure will be used for the analyses based on proportion of EGSS successes wherein the ANCOVA analysis is replaced with a logistic regression analysis. Specifically, missing 12 week EGSS values from which the dichotomized EGSS is derived will be estimated by (MCMC) which does not rely on the assumption of data missing at random. Additionally, the pattern of missing observations in each treatment group cannot influence the missing value estimation in the other because the imputation is being conducted independently for each treatment group.

The missing 12 week EGSS values will be derived for the analysis using the method of Markov Chain Monte Carlo (MCMC) multiple imputation. Multiple imputation and subsequent analysis will involve 4 principal tasks:

1. Calculate the number of missing values to be estimated by MCMC (nmiss) for 12 week value.
2. Create a data set, one for each treatment group, of subjects with observed values and those needing estimation by MCMC. The missing EGSS values in each data set will be filled in using the MCMC method ‘5 x nmiss’ times to generate ‘5 x nmiss’ data sets. The resulting data sets for each treatment arm will be combined into one complete data set by imputation.

Syntax:

```
proc mi data=datain out=dataout seed=&seed. nimpute=5xnmiss <options>;
  where trtpn=(1, or 2);
  mcmc chain=multiple;
  var baseline week4 week8 week12;
```

run;

3. For each complete data set, the dichotomous success rate (clear or almost clear with a 2-point change from baseline) will be computed. The 12-week estimated global values will be rounded to the nearest integer value prior to evaluating the success rate. Each complete data set will be analyzed with a logistic regression with factors of treatment group and analysis center.
4. The results from these analyses will be combined into a single inference using SAS PROC MIANALYZE.

A total of 2 random seeds will be needed to impute EGSS for the two treatment groups. Those 2 random seeds have been pre-specified by using a random number generator:

- EGSS; IDP-121 Lotion: Seed= 1210644108
- EGSS; IDP-121 Vehicle: Seed= 763715437

